9.4. SARS-CoV-2 POCT

If a participant has had onset of symptoms of CA-ARTI within 5 days of the baseline visit they will be invited to have a SARS-CoV-2 POCT (BD Veritor™ System for Rapid Detection of SARS-CoV-2 — see appendix C for more information on the test). The amount of antigen in a sample may decrease as the duration of illness increases so specimens collected after day 5 of illness are more likely to be negative compared to a RT-

PCR assay. Participants with symptoms for more than 5 days will not have the SARS-CoV-2 test but will continue with the baseline visit and randomisation.

This test is CE marked and will be used within its intended use. Clinicians will be provided with information and training on how to perform the test by the study team or their local co-ordinating centre with the assistance of the test manufacturer (training will be given according to the manufacturers kit instructions for use). Nasal swab specimens will be collected from the participant for analysis. The specimen collection, processing and test procedure will be according the manufacturer's instructions (see appendix C for more information).

If the test result is negative the participant will continue in the trial and be randomised as described in section 9.5. If the test result is positive, the GP will manage the participant according to national guidelines, they will record the test result on the baseline CRF. The participant will have completed participation in the trial and will be excluded from any further trial procedures.

Note/ this procedure has been added into the clinical algorithm in light of the COVID-19 pandemic. The SARS-CoV-2 test may not be included in the trial if test availability is too low or the test is not required due to low prevalence of the disease.

9.5. Randomisation

See section 11.2 for randomisation and stratification details.

If the participant has had symptoms for more than 5 days, or, the participant has had the BD Veritor™ SARS-CoV-2 POCT (section 9.4) and tested negative they will continue with trial randomisation. At the baseline visit the recruiter will enter the participant's baseline data into the online system, which will then enable the randomisation to take place. The randomisation process will take only a few moments via the online system and will not delay trial participation. The Data Monitoring Committee will ensure that the randomisation design will be executed as planned.

9.6. Blinding and code-breaking

PRUDENCE will be an open trial. The participant and the recruiting clinician will know the participant's allocation. Therefore, no unblinding or code breaking is required in the event of a relevant emergency.

The trial team and recruiting clinicians will be blind to emerging results. During the course of the trial, only those on the Data Monitoring Committee will have access to the unblinded data as part of the interim analysis.

9.7. Description of study intervention(s), comparators and study procedures (clinical)

9.7.1. Description of study intervention(s)

The interventions will be usual care (see section 9.6.2) with the addition of clinical algorithms (flow chart) including a CA-ARTI-Dx, details of the current clinical algorithm (flow chart) and diagnostic tests under evaluation can be found in the appendices.

9.7.2. Description of comparator(s)

Usual care of eligible patients with CA-ARTI consulting in primary care (e.g. general practices, LTCF, and primary care paediatricians) where the clinician is considering or going to prescribe an antibiotic. Clinicians will be referred to local guidelines for managing common infections where available.

9.7.3. Description of study procedure(s)

Clinicians will be provided with information and training on how to perform the CA-ARTI-Dx tests by the study team or their local co-ordinating centre with the assistance of the test manufacturer (training will be given according to the manufacturers kit instructions for use). Guidance for clinicians on how to respond to the test result are included in the clinical algorithm (study flow chart) for the diagnostics under evaluation in appendix B.

Depending on the outcome of the independent Data Monitoring and Ethics Committee (DMEC) review after period 1, additional CA-ARTI-Dx algorithms may be evaluated in period 2.

All interventions are CE marked and will be used within the scope of their intended use.

9.8. Baseline Assessments

After obtaining consent, the recruiter will complete the web-based baseline Case Report Form (CRF). The first part of this CRF will include: baseline demographic variables; comorbidities and relevant medical history; clinical severity and duration of symptoms. They will follow the clinical algorithm (study flow chart) outlined in appendix B, explaining and performing the SARS-CoV-2 test procedure if applicable If the participant is eligible to continue to randomisation, the responsible clinician's initial working diagnosis (before CA-ARTI-Dx if applicable); and responsible clinician's initial prescribing decision (before CA-ARTI-Dx if applicable) will be recorded on the baseline CRF. The recruiter will create equipoise for the participant about the randomisation process and allocation to different arms. All recruiters will be trained by the local PRUDENCE co-ordinating centre teams in how to do this as part of the trial training. They will continue to follow the clinical algorithm (study flow chart) outlined in appendix B, either their usual care process or one of the CA-ARTI-Dx strategies with usual care according to the participant's group allocation. Clinicians will be asked to refer to local guidelines for managing common infections for usual care, and be provided with the CA-ARTI-Dx strategies (clinical algorithm/flow chart outlined in Appendix B) as well as kit instructions/manuals on how to perform the CA-ARTI Dx for the intervention arms. The biological sample (e.g. finger prick blood test, nasal swab) required for the CA-ARTI-Dx will be taken in patients randomised to care with the addition of that CA-ARTI-Dx. Once the CA-ARTI-Dx test is complete (or the participant tested positive for SARS-CoV-2 so did not complete randomisation) the clinician will complete the second part of the baseline CRF.

Baseline CRF data items to be collected will include:

Part 1:

• Baseline demographic variables

- Comorbidities and relevant medical history
- Clinical severity and duration of symptoms
- BD Veritor™ SARS-CoV-2 POCT result (if applicable)
- Responsible clinician's initial working diagnosis (before CA-ARTI-Dx if applicable)
- Responsible clinician's initial prescribing decision (before CA-ARTI-Dx if applicable)

RANDOMISATION

Part 2:

- CA-ARTI-DX result (if applicable)
- Responsible clinician's final working diagnosis (after CA-ARTI-Dx if applicable)
- Responsible clinician's final prescribing decision (after CA-ARTI-Dx if applicable)
- Antibiotic prescription details: class, whether 'delayed' or for immediate consumption (if applicable)
- Any other medication prescribed and advised
- Information about any additional usual care advice given to the participant
- Information about any additional diagnostic/laboratory tests requested

With the exception of participants that tested positive to SARS-CoV-2, the recruiters will provide all other participants with instructions on completing a simple, user-friendly diary to be completed over 14 days from the baseline visit (day 1). Contact details will be collected from these participants including mobile/home telephone numbers and email addresses to enable the collection of the follow-up data.

9.9. Subsequent Visits

There is no requirement for participants to have a research-specific face-to-face follow-up visit as part of their study participation, as all subsequent measurements consist of self-completed questionnaires or through telephone calls by the trial team (including process evaluation interviews for some of the participants).

Participants (or their legal guardian or their carer) will be asked to complete a simple, user-friendly diary each day until they have returned to usual activity for two consecutive days, or up to day 14 (whichever is sooner), the diary will request the following information:

- Employment status
- Return to usual activities each day
- Antibiotic use
- Use of other prescription medication
- Individual symptom severity
- Health care resource use, including hospitalisation
- Use of over-the-counter and non-prescription medication or remedies
- Out-of-pocket expenditure
- Number of work/school/nursery days lost
- EQ-5D-5L (or alternative as recommended for age) and Visual Analogue Scale (VAS) (Day 1, Day 14 and Day 28)
- Patient Enablement Instrument (Day 1)

• Process evaluation patient survey (see section 9.10) (Day 1)

The diary will be available on-line (study team preferred option) and in a paper version for posting back to the national network coordinator when specifically requested or where the participant does not have daily access to the internet.

Participants who have not completed/returned their diary by day 14 will be telephoned on or after day 14 (+ 3 days) by the study team and asked a brief set of questions to establish a minimal data set including antibiotic use, day returned to usual activity, hospitalisation, COVID-19 testing and EuroQoL EQ-5D. All participants will be telephoned again on or after day 28 (+ 3 days) regarding antibiotic use, day returned to usual activity if not already stated by day 14, hospitalisation, COVID-19 testing and EuroQoL EQ-5D in the preceding 14 days. We will also repeat the brief process evaluation patient survey (see section 9.10). The study team will attempt to call the participant no more than 3 times on each occasion.

Participants may receive reminder text messages about these telephone calls and to return the diary if they give the trial team their mobile telephone number.

Participants who have visited hospital with complications related to CA-ARTI and who have had a chest X-ray may have their clinical record in primary care examined by the study team for confirmation of diagnoses of complications including pneumonia.

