11.3. Co-Primary Endpoints

The study has two co-primary endpoints:

- 1) Whether a participant is prescribed at least one antibiotic course (of any dose or duration) over 28 days from inclusion (yes/no)
- 2) Time to return to usual daily activities (in days)

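### Follow-up under Section 9.9 asks about antibiotic use, and read literally leaves days unasked, although co-primary 1 is any antibiotic prescribed over 28 days; some later prescriptions can be scored as none

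*Protocol*

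**What the plan says.** Section 11.3 defines the first co-primary endpoint as "Whether a participant is prescribed at least one antibiotic course (of any dose or duration) over 28 days from inclusion (yes/no"). Section 6 gives its sources as the day 1 to 14 diary or the day 14 call, plus the day 28 call. It gives the same sources for the secondary outcome on antibiotic class and delayed or immediate prescribing, and lists antibiotic use over 28 days as a separate secondary outcome.

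The data collection is described as follows.

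- **Baseline (Section 9.8):** the form records the final prescribing decision and "Antibiotic prescription details: class, whether 'delayed' or for immediate consumption (if applicable"). Appendix A marks prescription details on Day 1 only.
- **Diary:** Section 9.9 asks for a "diary each day until they have returned to usual activity for two consecutive days, or up to day 14 (whichever is sooner"), with antibiotic use among its items. Section 9.8 describes a "simple, user-friendly diary to be completed over 14 days from the baseline visit (day 1"). The item list in Section 9.9 also puts an EQ-5D on Day 14.
- **Day 14 call (Section 9.9):** "Participants who have not completed/returned their diary by day 14 will be telephoned on or after day 14 (+ 3 days"). The antibiotic item is again use.
- **Day 28 call (Section 9.9):** "All participants will be telephoned again on or after day 28 (+ 3 days) regarding antibiotic use, day returned to usual activity" if not already known, then "hospitalisation, COVID-19 testing and EuroQoL EQ-5D in the preceding 14 days".

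Review of primary care records is limited to participants who visited hospital with complications and had a chest X-ray, and serves to confirm complications.

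**The concern.** There are two separate problems.

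The first is what is asked. A delayed prescription issued on day 1 is an event whether or not it is taken. One issued on day 9 and never taken has no listed field, because every later contact asks about use. As itemised, the endpoint changes from prescribing to use after baseline.

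The second is when it is asked. A participant back to usual activity on day 4 completes the diary on day 5. If that diary counts as completed, there is no day 14 call, and a 14-day look-back from day 28 begins at about day 14. A course prescribed and finished in between is not asked about.

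What is at stake is the reason for a 28-day window: to tell prescribing that is avoided from prescribing that is only postponed. Missed late prescriptions would be recorded as a no, not as missing. Neither the complete-case analysis in Section 11.9 nor the 5% missing-endpoint allowance in Appendix F deals with them, and data never asked for cannot be recovered at analysis.

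**Working it through.** **1. The plan's own figure.** Section 11.6 gives 100 per arm (80% power) and 133 per arm (90% power) for 90% against 75% at two-sided 0.05. With pooled variance, n = [1.96·√(2·0.825·0.175) + z·√(0.9·0.1 + 0.75·0.25)]² / 0.15².

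- z = 0.8416: (1.0532 + 0.4433)² / 0.0225 = 99.5, so 100.
- z = 1.2816: (1.0532 + 0.6751)² / 0.0225 = 132.8, so 133.

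Both reproduce. The problem is measurement, not sample size.

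**2. How often the diary would stop early.** Inputs: exponential recovery time with a mean of 4 days (Section 11.6) and the stopping rule in Section 9.9. I assume whole days: first usual activity on day T, diary ending on day T + 1. It ends before day 14 if T ≤ 12:

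P(T ≤ 12) = 1 − e^(−12/4) = 1 − e^(−3) = 0.950.

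In continuous time with a one-day lag, it is 1 − e^(−13/4) = 0.961. An early stop is the usual course on the protocol's assumption.

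**3. Length of the stretch from diary stop to day 14.** In whole days the mean is the sum over k = 1 to 12 of (1 − e^(−k/4)) = 12 − 3.35 = 8.65 days, and 8.65 / 0.950 = 9.1 days among those who stop early. In continuous time it is 13 − 4 × 0.961 = 9.2 days (one-day lag) or 12 − 4 × 0.950 = 8.2 days (two-day lag). So it is about 8 to 9 days.

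**4. Effect of a late call.** The day 28 call may be made up to day 31. Since 31 − 14 = 17, a 14-day look-back then starts at day 17. Even a full 14-day diary would leave the days between 14 and 17 unasked.

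**5. Which prescriptions can be lost.** Baseline prescriptions are captured. Later courses taken while the diary runs, or within the day 28 look-back, appear as use. What can be lost is a first prescription issued and finished in the gap, and any post-baseline prescription never taken.

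**6. Direction.** Let d be the share of an arm not prescribed on day 1, and m the share of those whose only prescription is missed. The reduction is overstated by d(test)·m(test) − d(control)·m(control). With a common m this is m × [d(test) − d(control)]: zero if day-1 prescribing is equal, positive if the test arms prescribe less on day 1. As m runs from 0 to 1, it ranges from nothing to the whole day-1 difference. The documents give neither d nor m, so no point within that range can be chosen.

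**The case against.** The strongest reply is that the text does not firmly establish the gap. Section 9.8 has the diary run over 14 days, Section 6 and Appendix A label it as covering days 1 to 14, and its Day 14 EQ-5D presupposes that it is still open. The look-back phrase in Section 9.9 may attach only to EQ-5D. It is not stated whether a diary stopped early counts as completed for the day 14 call. Section 6 does assign prescribing, class and delayed status to follow-up, so the item lists may be shorthand; the diary and call scripts are not at hand. People already back to usual activity may also rarely need a new prescription.

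Much of this stands. The time gap is one literal reading of inconsistent text, and it largely closes if the 14-day diary governs. But no longer look-back for antibiotics is stated anywhere, and none of these points supplies a prescribing item after day 1.

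A reader might infer three stronger things, which the documents do not support:

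- **That hospitalisations fall into the same gap.** Section 10 requires all serious adverse events over the 28 days, which include inpatient admissions, to be recorded. Appendix A also marks hospital admissions in the Day 28+ retrospective column.
- **That the bias can be computed from 90% and 75%.** These are 28-day rates. Under them, the remaining 10% and 25% are never prescribed within 28 days and so cannot have a late first prescription. They are not day-1 rates.
- **That false superiority is likely.** This requires losses concentrated in the test arms, which no figure in the protocol supports. At the planned 15-point effect, Appendix F states more than 99% power in a single season, so a modest loss would affect the estimated reduction more than the superiority conclusion.

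**Conclusion.** The point holds as a mismatch that should be fixed. The endpoint is prescribing over 28 days, while the itemised follow-up records use. Sections 9.8 and 9.9 disagree on how long the diary runs, and the literal reading of Section 9.9 leaves an early-recovering participant without a scheduled antibiotic question until about day 14, or day 17 if the final call is made on day 31.

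Under the protocol's exponential mean of 4 days, about 95% of participants would reach the early stop. That figure measures how many are exposed to the gap, not how many prescriptions are lost. Some later prescriptions can be missed; it does not follow that late prescriptions in general are.

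The likely direction is an overstated reduction. This depends on test arms having more participants without a day-1 prescription and on a similar miss rate across arms. The size is unknown.

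**What to change.** 1. Reconcile Sections 9.8 and 9.9 on diary duration, and state whether a diary stopped early counts as completed for the day 14 call.
2. At the day 28 call, ask every participant about any antibiotic prescribed since the last diary entry, or since inclusion if there is none, up to day 28. Record the date, whether immediate or delayed, and whether taken. This replaces reliance on a 14-day look-back for this endpoint.
3. Add an antibiotic-prescribed item, separate from use, to the diary and to the day 14 and day 28 calls, in Section 9.9 and Appendix A, so that they match Sections 6 and 11.3.
4. Schedule the day 14 EQ-5D for participants whose diary ended early.

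The cost is a minor amendment, revised wording in the diary, call script and electronic form, and slightly longer recall at day 28. No extra contact is needed apart from an online EQ-5D prompt for early stoppers. Only participants followed up after the change would benefit.

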When clinical trials of the cost-effectiveness of POCTs have been done, trials have generally adopted a traditional two arm approach, which can be inefficient. Innovative trial designs could allow greater efficiency flexibility, for example evaluating more than one intervention and replacing or adding new interventions within the same trial. Critically, CA-ARTI-Dx should better target antibiotic prescribing and use, thus reducing the overall amount of antibiotics used. However, this should not be at the expense of patient recovery. Evaluations should ensure that the introduction of any new CA-ARTI-Dx is based on evidence for reduced antibiotic use/prescribing and evidence that use of the CA-ARTI-Dx does not cause patients harm.

A pragmatic trial

The aim of PRUDENCE is to determine the value of the information of having a CA-ARTI-DX result available at the point of making a prescribing decision in addition to usual care clinical assessment. (without a CA-ARTI-Dx), in situations where a CA-ARTI-Dx result could sway the responsible clinician towards not

prescribing an antibiotic which does not result in harm to the patient (increased symptom duration or severity). When there is no doubt in the clinician's mind that antibiotics are definitely not indicated, such as in the case of an obvious viral, self-limiting infection, then performing a test does not influence clinician uncertainty and so should not be performed. Testing everyone with CA-ARTI in primary care is neither feasible nor appropriate. Thus, we wish to include only those patients in whom the responsible clinician is considering or planning to prescribe an antibiotic, and exclude those where they feel an antibiotic is not indicated. Given that the comparison will be to management without a CA-ARTI-Dx result, the trial should be as minimally disruptive to usual care as possible.

Due to uncertainties around COVID-19, the study may be paused in certain networks/regions if it is not feasible to proceed according to this pragmatic protocol.

COVID-19

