6. OBJECTIVES AND OUTCOME MEASURES

Objectives		Ou	tcome Measures	Timepoint(s) of evaluation of this outcome measure (if applicable)			
Co-primary: To assess effectiveness of CA-ARTI-Dx in terms of both reductions in antibiotic prescribing, and in terms of patient recovery.		The proportion of participants being prescribed at least one antibiotic course (of any dose or duration) over 28 days from inclusion (estimating possible reduction). Time to return to usual daily activities, where returned to usual daily activity = yes (estimating non-inferiority)		Day 1 – 14 diary or Day 14 telephone call, and Day 28 telephone call			
	ondary: explore whether adding a CA-						
1) 2) 3)	Additional effects on antibiotic prescribing Effects on antibiotic use Effects on patient recovery and safety, including complications and hospitalisation	1) 2) 3)	Choice of antibiotic class, whether 'delayed' or immediate Antibiotic use over 28 days after inclusion. Patient reported symptoms severities, re-consultations, hospitalization, pneumonia	2)	Day 1 – 14 diary or Day 14 telephone call, and 28 telephone call Day 1 – 14 diary or Day14 telephone call,		
4)	Effects on use of medications other than antibiotics	4)	Use of other, non-antibiotic, medication including antiviral medication, and over-the-counter treatments.	3)	and 28 telephone call Day 1 – 14 diary or Day 14 telephone call, and 28		
5)	Effects on clinician's decision making process regarding diagnosis and treatment	5)	Responsible clinician's initial working diagnosis and antibiotic prescribing decision before test, if randomised to CA-ARTI-Dx also final decision after test.	4)	telephone call Day 1 – 14 diary or Day 14 telephone call, and 28 telephone call		
6)	Effects on patients' perceived ability to understand and cope with their illness	6)	Patient Enablement Instrument (PEI) score.	5) 6)	Baseline visit Day 1 -14 diary		

7)	Is cost effective	7)	Costs data: EQ5D at day 1, Day 14 and Day 28; time taken for testing; costs associated with subsequent help seeking, complications, work loss and over-the-counter medication use (to be determined in close collaboration with WP5).	7)	Baseline visit, Day 1 – 14 diary or Day 14 telephone call, and Day 28 call
То	identify:	1)	Interviews and surveys with		
1)	Clinicians' views and experiences of CA-ARTI-Dx and how they fit with/impact on delivery of care and intended future use.	1)	healthcare professionals.		

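### Daily symptom recording stops when the participant resumes usual activity and no item records when symptoms resolve, so symptom duration, part of the protocol's own definition of harm, cannot be compared in all randomised participants

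*Protocol*

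**What the plan says.** **Aim.** Section 5 (A pragmatic trial) looks for a move away from prescribing "which does not result in harm to the patient (increased symptom duration or severity").

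**Outcome.** Section 6 lists under patient recovery and safety: "Patient reported symptoms severities, re-consultations, hospitalization, pneumonia". Its timepoints are the diary or day-14 call, and the day-28 call.

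**Diary.** Section 9.9 includes "Individual symptom severity" among the diary items and has the diary kept "until they have returned to usual activity for two consecutive days, or up to day 14 (whichever is sooner"). Section 9.8 describes a "diary to be completed over 14 days from the baseline visit (day 1") and mentions no early stop.

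**Day-14 call.** Section 9.9: "Participants who have not completed/returned their diary by day 14 will be telephoned". They are "asked a brief set of questions to establish a minimal data set including antibiotic use, day returned to usual activity, hospitalisation" and a few further items. Symptoms are not named.

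**Day-28 call.** This goes to all participants, "regarding antibiotic use, day returned to usual activity if not already stated by day 14, hospitalisation, COVID-19 testing and EuroQoL EQ-5D". Symptoms are again not named.

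**Schedule.** Appendix A marks symptom severity at baseline, in the diary, at the day-14 call and at the day-28 call.

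**The concern.** The stopping rule for the symptom diary is return to usual activity, which is the second co-primary endpoint. Resuming activity is not the same as being free of symptoms. Participants enter with cough or sore throat, and either can outlast the return to work, school or normal routine. For such a participant the protocol records neither the course of symptoms after the diary closes nor the day on which they ended.

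Two things are at stake. First, symptom duration is one half of what section 5 calls harm, and it cannot be compared across all randomised participants. A test arm with a similar return to activity but a longer cough could meet the non-inferiority criterion without the difference showing. Second, daily severity scores on later days exist only for participants who recovered more slowly. That group is selected by a post-randomisation outcome, and its size can differ between arms.

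This is a matter of data collection, which the protocol fixes. No analysis plan can recover days that were never recorded.

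**Working it through.** **1. The protocol's recovery model.** Section 11.6 assumes exponential recovery with a mean of 4 days, a margin of 1 day (mean 5, hazard ratio 4/5 = 0.80), 80% power and two-sided alpha 0.05, and gives 318 per group. Freedman's formula for total events is (1.960 + 0.842)² × [(1 + 0.8)/(1 − 0.8)]² = 7.849 × 81 ≈ 636, or 318 per group. The stated figure reproduces exactly. Schoenfeld's formula gives 631 events, about 316 per group. The same model can therefore be used to see how long the diary runs.

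**2. Share still keeping the diary.** Let T be the time to return to usual activity, with mean m. The diary closes two days later, so a participant is still recording on day t if T > t − 2. The share is exp(−(t − 2)/m). Counting in whole diary days gives the same shares.

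| Day | m = 4 | m = 5 |
|---|---|---|
| 5 | exp(−3/4) = 47% | exp(−3/5) = 55% |
| 7 | exp(−5/4) = 29% | exp(−5/5) = 37% |
| 10 | exp(−8/4) = 14% | exp(−8/5) = 20% |
| 14 | exp(−12/4) = 5% | exp(−12/5) = 9% |

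So 71% (m = 4) or 63% (m = 5) have closed the diary before day 7, and 95% or 91% before day 14. The mean diary length, 2 + m × [1 − exp(−12/m)], is about 5.8 days of 14 at m = 4 and about 6.5 at m = 5.

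**3. Difference between arms.** With control at mean 4 and a test arm at the margin (mean 5), 29% and 37% would still be recording on day 7. Those observed on later days would not be comparable groups.

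**4. What the other contacts add.**

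- *Day-14 call:* it goes only to those without a completed or returned diary. A participant who stopped early as instructed would appear to have completed it and would get no call.
- *Day-28 call:* it reaches everyone. Appendix A and the section 6 table place a severity rating there, but section 9.9 omits it. One rating at day 28 shows whether symptoms are present then, not when they ended.
- *Resolution day:* no section asks for it.

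**5. Sections that disagree.** Section 9.8 has a 14-day diary, and section 9.9 stops it early. Section 9.9 also lists a day-14 EQ-5D among the diary items, which an early stopper would not reach. Appendix A and the section 6 table put symptom severity at the calls, and the call content in section 9.9 does not name it.

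**The case against.** The strongest reply is that symptoms are not lost for recovered participants. They rate symptoms daily until they recover and through the two qualifying activity days. Appendix A and the section 6 table then schedule a severity rating for everyone at day 28. The day-14 list in section 9.9 is introduced as non-exhaustive, so its silence on symptoms proves little. Re-consultations, hospitalisation, pneumonia and EQ-5D also bear on harm. The definition of harm stands in the background section, the listed outcome is severities rather than duration, and a short diary suits a pragmatic trial.

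Much of this stands, and it rules out several stronger readings that a reader might infer:

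- *That symptoms go unobserved once a participant recovers.* The day-28 rating and the two activity days contradict this. On day 7 at mean 4, 28.7% are still recording but only exp(−7/4) = 17.4% have not recovered. The rest are in their two activity days.
- *That severity will be compared only among the unrecovered.* No such analysis is stated, and section 11.10 leaves secondary analyses to the SAP.
- *That most symptom-days are lost.* The shares above concern diary days under a planning assumption. The protocol gives no distribution of symptom duration, so the share of symptomatic days missed cannot be calculated.
- *That the trial cannot address harm at all.* The other safety outcomes and the day-28 rating say otherwise.

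The reply does not supply a record of symptom course between diary closure and day 28, or of the resolution day, and it does not reconcile sections 9.8 and 9.9 with Appendix A.

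**Conclusion.** The point holds in a limited form. Return to activity cuts off daily symptom recording, and no item captures when symptoms resolve. Symptom duration therefore cannot be compared across all randomised participants, although section 5 names it as harm. Daily severity on later days is available only for slower recoverers: about 29% of participants on day 7 and 5% on day 14 at a mean of 4 days, or 37% and 9% at a mean of 5 days.

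These shares rest on the exponential recovery assumption in section 11.6 and on participants stopping the diary as section 9.9 instructs. They do not show how many participants still have symptoms when they stop. The day-28 severity rating is scheduled but is missing from the call content in section 9.9. The return-to-activity endpoint, its margin and its sample size are unaffected. The change is worth making because it is cheap and lets the trial speak to symptom duration.

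**What to change.** 1. Reconcile section 9.8, section 9.9, Appendix A and the section 6 table: one rule for diary length, and one list of what each call asks, with symptom severity named if it is meant to be collected there.
2. Capture symptom duration in one of two ways:
   - separate the symptom items from the activity stop, so that they continue to day 14, or until symptoms resolve, whatever the activity status; or
   - add to the day-28 call, already made to everyone, the day on which the main symptom (cough or sore throat) resolved.
3. Name symptom duration as a secondary outcome, compared as time to event in all randomised participants.

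The first option costs a change to the diary logic and slightly more burden on participants. The second costs one question, with recall error in the reported day. Neither touches the co-primary endpoints or the sample size.
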